6.2 Storage and operating information

Operating temperature: +15°C to +30°C

Controller and headband storage and transportation temperature: -20°C to +50°C

Catheter storage and transportation temperature: +5°C to +40°C

Humidity (all conditions): 20% to 80% RH non-condensing

Operating altitude: -300 m to 2500 m

Controller input mains: 100-240 V ~, 50/60 Hz, 115VA; Protective ground

Classification: Controller and catheter: Medical Device Directive (MDD) Class IIa

Headband: MDD Class I

6.4 Indication

In this clinical investigation, the Chordate System S211 is intended to be used for the treatment of adult subjects (18 to 65 years) with chronic migraine.

7 Justification for the design of the clinical investigation

7.1 Pre-clinical experiences and biocompatibility

Pre-clinical investigations in animals have not been conducted since there is no appropriate animal model for this treatment.

The subject is not in contact with the Chordate Controller and no biocompatibility evaluation is needed. The only parts in contact with the subject are the balloon part of the catheter and the consumables; medicinal liquid paraffin and the hair net positioned under the head band. For the latter, CE-marked products for medical use will be used.

The balloon in the catheter is made from protective gloves (polyvinylchloride) that are CE-marked according to the Medical Device Directive class I and apply to EN 455-1-4. The balloon is in contact with the subject's mucosal membrane in the nasal cavity for transient use. The material (polyvinylchloride) is well known and data regarding the biocompatibility are given by the manufacturer. There are no biocompatibility issues during the transient use of the catheter.

7.2 Clinical experience

The Chordate System S211 is not yet CE-marked for migraine. However, promising results with predecessor Chordate System models were reported in early clinical studies.

The Chordate System is CE-marked for rhinitis. Two double-blind controlled clinical trials including 80 subjects with non-allergic rhinitis and rhinitis medicamentosa showed efficacy on nasal obstruction, secretion, and for some subjects itching [7].

One safety and tolerability study (PS002) with the Chordate System in 12 healthy subjects showed that the treatment was safe and well tolerated.

A double-blind study (PR003) in 207 patients with non-allergic rhinitis demonstrated that the Chordate system was more efficacious than placebo in reducing the weekly mean Total Vasomotor Rhinitis Symptom Score. There were no safety concerns. One serious adverse event (SAE) i.e. stroke two weeks after treatment has been reported but was judged to be not associated with study treatment.

So far, 2 studies with the Chordate System were performed in migraine patients (PM004 and PM005). Both studies were randomized, placebo-controlled, double-blind, multicenter studies to evaluate the performance and safety of the Chordate System.

Study PM004 investigated the effect of the Chordate System on acute migraine. In total, 51 patients with acute migraine attacks of moderate to severe intensity were enrolled. No statistically significant effects of the Chordate System on acute migraine headache pain and migraine features (pain-free rate, sustained pain free rate, time to meaningful relief, migraine associated symptoms, migraine derived disabilities, or global impression) were shown. A total of 42.3% in the active group and 32.0% in the placebo group showed headache relief. Rescue medication was taken by 57.7% subjects in the active group and 64.0% in the placebo group at 24 hours after treatment. A slightly higher proportion of patients with meaningful pain relief was observed in the active group compared with the placebo group.

Study PM005 investigated the potential prophylactic effect of 2 treatments with the Chordate System at an interval of 2 weeks. A total of 78 subjects were included in the performance analysis. There was no statistically significant effect on migraine frequency (days) during the complete 3 months after treatment. However, the Chordate system showed a close to significant ($p=0.0515$) effect on migraine frequency (days) 2 months after treatment.

In both migraine studies, treatment with the Chordate System was generally well tolerated. Mild transient effects on nasal and tear secretion, paresthesia of the lip, burning sensations and slight discomfort and pain were observed.

For more information please see the IB.

7.3 Justification for the clinical investigation

Migraine is a common neurological syndrome that affects approximately 10-20% of the population. The pathophysiological mechanisms leading to migraine are still poorly understood. Despite recent progress in pharmaceutical interventions to treat and prevent migraine attacks, the efficacy of these drugs is poor. In addition, for certain patients these drugs have many side effects, resulting in a large proportion of patients discontinuing the drugs. Thus, new treatment approaches are urgently needed. A drug-free approach like the Chordate System may provide a novel effective treatment and preventive measure with fewer adverse events (AEs).

The aim of this clinical investigation is to investigate the potential prophylactic effect of Chordate System treatment on migraine headache.

A randomized double-blind study with a placebo control was deemed appropriate to control for all potential influences. The concurrent placebo control group will be drawn from the same subject population as the active group. Random treatment assignment and double blinding will be used to minimize the chance of selection bias and to ensure that the active and control groups

will be similar at the start of the study and will be treated similarly during the course of the study.

8 Risks and benefits of the investigational device and clinical investigation

8.1 Potential risks

A risk analysis for the Chordate System S211 showed that the system is free from unacceptable and undesirable risks.

Results of the risk assessment are provided within the IB. For this study, eligibility criteria have been incorporated to avoid identified potential safety issues. The risks and mitigation procedures established are summarized below.

Potential risk	Mitigation
Hypersensitivity to polyvinylchloride or medicinal liquid paraffin.	Subjects with allergies to the materials of either device will be excluded.
Risks relating to biocompatibility with the Headband (allergic reaction, cross-contamination between subjects and risk of hair becoming caught in device).	A fresh hair net will be used for each subject.
Potential for risk of overtreatment and damage to nasal mucosa.	Treatment has been confined to a maximum of 20 minutes.
Small amounts of blood have occasionally been observed on the protective glove.	Subjects with a history of nose bleeds (epistaxis) and concomitant conditions that could cause excessive bleeding have been excluded. Treatment will be halted if a subject experiences a nose bleed during treatment.
In subjects with a pronounced anterior septal deviation, the balloon may be difficult to insert and the treatment be painful on the narrow side.	Subjects with a pronounced deviation will be excluded from the study.
Possible risk of complications in subjects with an implantable stimulator.	Subjects with any active implantable devices in the head and/or neck, will be excluded.
Subjects who have received radiation to the face or previous sinus surgery may have scarring and more fragile tissues which may increase the risk of bleedings and tissue damage during treatment.	Subjects with radiation to the face or who have undergone previous sinus surgery will be excluded.
Ongoing infection or malignancy of the nasal passage may prevent a therapeutic effect and increase the risk of complications during therapy.	Subjects who have been diagnosed with nasal malignancy will be excluded from the study. Subjects with an ongoing nasal infection will be excluded from treatment.

Although there are no anticipated risks to mother or fetus, women who are pregnant or at risk of being pregnant at the time of treatment will also be excluded.

The following device-related effects were observed during treatment with the Chordate System. These effects are not serious, but could be perceived as disturbing.

The following adverse device effects (ADE) are anticipated during the insertion of the catheter in the nasal cavity:

- Slight discomfort
- Slight pain
- Mild burning sensation
- Sneezing
- Increased tear secretion

The following ADEs are considered anticipated during treatment with the Chordate System:

- Sneezing
- Increased nasal secretion
- Increased tear secretion
- Paresthesia of the lip
- Slight pain
- Slight discomfort
- Mild burning sensation
- Minor epistaxis (at withdrawal of catheter)

All these effects are short-lasting and cease within a few minutes after treatment completion. As these are anticipated effects, if symptoms are mild, these should not be reported as an AE or ADE. However, if these are moderate or severe, these must be reported as AE or ADE.

8.2 Potential benefits

Anecdotal evidence has pointed to a potentially positive effect of treatment with the Chordate System on migraine frequency.

A recent randomized, placebo-controlled, double-blind pilot study to investigate the potential prophylactic effect of 2 treatments with the Chordate System S200 at an interval of 2 weeks did not show a statistically significant effect on migraine frequency (days) during the complete 3 months after treatment; however, a close-to-significant effect on migraine frequency (days) was observed 2 months after treatment.

The anticipated benefits of treatment within this clinical investigation include:

- Reduced frequency and/or severity of migraine attacks, which in addition to improving subject's quality of life, could also potentially reduce the amount of medication(s) required and associated risks related to these.

- Potential improvement of the situation for patients who cannot currently tolerate other pharmaceutical treatments due to drug interactions or comorbidities.
- For subjects not already keeping a migraine diary, collecting diary data for the clinical investigation may help in their migraine diagnosis and ongoing care.

8.3 Risk benefit rationale

No hazards were found to present unacceptable risk levels when some risks are reduced further by proper use, handling and maintenance of the system. All users of the investigational device will be trained prior to administering treatment.

There are no residual risks of the device used in this clinical investigation that have not been controlled within the IFU.

Beyond the application of the medical device system under investigation, the protocol-mandated measures imposed to the subjects virtually are associated with no additional risks.

In conclusion, the possible benefits of the clinical investigation justify the potential risks.

9 Investigators and administrative structure of the clinical investigation

The study is planned to be conducted at 5 centers in Germany and max. 6 centers in Finland under the supervision of [name]. med. [name] (coordinating investigator).

The sponsor (Chordate Medical AB) will be responsible for the overall administration of the clinical investigation. FGK Clinical Research GmbH (in the following referred to as sponsor's representative), a contract research organization, will be responsible for project management, site monitoring, medical monitoring, handling and reporting of SAEs, serious adverse device effects (SADE), and device deficiencies and regulatory submissions.

Addresses and telephone numbers of the main responsible persons are provided in Section 4.

The study is supported by the Swedish Governmental Agency for Innovation Systems (<http://www.vinnova.se/en/>).

10 Objectives of the clinical investigation

Primary objective:

- To evaluate the effect of intranasal KOS using the Chordate System S211 on monthly headache days with moderate to severe intensity.

Secondary objectives:

- To evaluate the effect of treatment with the Chordate System S211 on monthly migraine days, responder rate, use of abortive medication, health-related quality of life and disability, and patient's global impression of severity;
- To evaluate the incidence and severity of AEs and ADEs following treatment with the Chordate System S211.

11 Design of the clinical investigation

11.1 General

11.1.1 Description of the design of the clinical investigation

This is a randomized, placebo-controlled, double-blind, multicenter clinical investigation of a medical device. The study consists of a 4-week screening period, a 6-week treatment period (2 weeks run-in and a 4-week observation window to assess the treatment effect), and a 4-week follow-up period.

Subjects who provided written informed consent and are eligible for the study will be asked to complete a daily diary for 4 weeks during the screening period. In the diary the subjects will record headache and migraine days, any changes in their health, and concomitant medications they may be using. The data collected in the diary during this screening period will be used as Baseline for the performance assessments.

Subjects who completed the screening period and continue to meet the eligibility criteria after review of diary entries by the investigator will be randomized (stratified by medication overuse) in a 1:1 ratio to receive either active or placebo treatment. The subjects will receive 6 treatments with the Chordate System S211 at weekly intervals at the site (Day 0 to 35; treatment Visit [V] 1 to 6) and continue to maintain a daily diary. One week after the last treatment, an end of treatment visit will be performed on Day 42 (V7).

After completion of the 6-week study treatment period (V1 to V7), subjects will be followed-up for another 4 weeks. The final visit will be performed on Day 70, 5 weeks after the last study treatment. During the 4-week follow-up, the subjects will continue to complete a daily diary.

11.1.2 Primary and secondary endpoints

Performance endpoints

Primary performance endpoint:

- Mean change from Baseline (4-week screening period) in monthly headache days with moderate to severe intensity in 4-week performance assessment period (V3 to V7).

Secondary performance endpoints:

- Mean change from Baseline in monthly headache days with moderate to severe intensity in follow-up period;
- Mean change from Baseline in monthly migraine days;
- Mean change from Baseline in monthly headache days (mild, moderate and severe intensity) in 4-week performance assessment period (V3 to V7);
- Proportion of subjects with 30% or greater reduction in headache days of moderate to severe intensity;
- Proportion of subjects with 50% or greater reduction of headache days of moderate to severe intensity;
- Change in the use of acute (abortive) medication;
- Change in migraine-specific quality of life questionnaire (MSQ), headache impact test-6 (HIT-6), and patient global impression of severity (PGI-S).

Safety endpoint

- Frequency, severity, device-relationship, and outcome of AEs.

All performance measurements used in this study are established migraine evaluations that have been validated as reliable and relevant. The measures of safety used in this study are routine clinical procedures.

11.1.3 Subject identification

Subjects will be assigned a unique 4-digit number, with the first 2 digits identifying the site and the last 2 digits identifying the subject, e.g. 01-01. At each site the investigator will assign numbers to subjects in ascending order e.g. 01, 02, 03 etc.

11.1.4 Duration of the clinical investigation

The overall duration of the clinical investigation including enrollment and treatment of all subjects is anticipated to be 1.5 years with an expected enrollment period of about 9 months.

The duration of the clinical investigation for each participating subject is about 14 weeks.

11.2 Treatments, precautions and restrictions

11.2.1 Investigational device

Packaging and labeling

The investigational device will be labeled according to applicable guidelines and national legal requirements.

Treatment settings and protocol

The investigational device will only be used as part of the clinical investigation. Treatment with the device will be in compliance with the clinical investigation plan (CIP) and manufacturer's IFU. Devices will be supplied to the site with pre-set pressure/frequency to be used for the clinical investigation. Any deviation from the prescribed technique and timing as described in the IFU will be recorded as a deviation. A comment explaining the deviation must be given within the paper case report form (pCRF).

The investigator will enter a 4-digit randomization number. The controller contains an internal programmable database, defining if a specific randomization number shall result in normal (active) treatment or placebo treatment (no oscillations).

Treatment time will be 10 minutes in each cavity (a total of 20 minutes per treatment) at 85 Hz and 80 mbar. Subjects should be in an upright position. First, the headband will be placed on the subject's head. The catheter's balloon part will be dipped in liquid paraffin and inserted into the subject's nostril (start on any side). The headband's fixation arm and catheter will be connected such that the catheter is kept in the correct position. For a detailed description please see the IFU.

The pre-set frequency (85 Hz) and pressure (80 mbar) will be used in the treatment of all subjects. All subjects should receive the pre-set 10 minutes of continuous treatment time per nostril. Once one nostril has been treated, the investigator will treat the other nostril with a minimum of delay.

11.2.2 Precautions and restrictions

Treatment with the Chordate System may not be performed in subjects with a body temperature $>38.5^{\circ}\text{C}$.

11.2.3 Methods of assigning subjects to device groups

Subjects will be randomly assigned in a 1:1 ratio to active or placebo treatment by means of a computer-generated randomization list. Randomization will be stratified by medication overuse (yes/no) at V1.

Medication overuse is defined as regular overuse for >3 months of one or more acute symptomatic drugs (according to the IHS classification):

- Ergotamine, triptans, opioids or combination analgesic medications on ≥ 10 days per month on a regular basis for >3 months;
- Simple analgesics or any combination of ergotamine, triptans, analgesics or opioids on ≥ 15 days per month on a regular basis for >3 months without overuse (≥ 10 days) of any single class alone.

The Chordate System S211 can deliver normal (active) treatment or placebo treatment. The user will enter the randomization number assigned to the patient before start of treatment, and based on a hidden randomization table; the controller will either deliver active or placebo treatment.

The controller acts in one of two modes:

- Active treatment: The controller creates air-mediated kinetic oscillations with regulated pressure and frequency during a preset treatment time.
- Placebo treatment: Placebo treatment is similar to active treatment, but with no oscillations.

It is difficult to discern any difference between active and placebo treatment.

11.2.4 Investigational medical device accountability

Shipment, receipt, and return of all clinical investigational devices will be tracked and documented by the monitor and investigator. Product name, amount, lot numbers, and expiry dates will be documented for investigational devices provided to each investigational site. The disposition of devices (used, not used, or returned) will be recorded. When the treatment period is complete or at the latest during the site close out visit, the monitor will ensure that all investigational devices are returned to the sponsor. As the treatment is administered by the investigator only, compliance will be controlled by the device accountability log. Single use products, i.e. hair nets and catheters, will be disposed at the sites according to local routine.

11.2.5 Previous and concomitant medications and treatments

Subjects must be on a stable prophylactic migraine medication regimen, if any, during the 3 months prior to screening and maintain this regimen (no change in type, frequency or dose) from screening to end of follow-up. No new prophylactic migraine medication may be initiated. Treatment with Botox is not allowed during the study (from screening to end of follow-up).

Medication, which is considered necessary for the subject's safety and well-being, may be given at the discretion of the investigator at any time.

Subjects can use their regular acute migraine medication, when necessary, during the course of the clinical investigation. However, all such use and any changes must be documented in the diary by the subjects.

The diary will be used to collect data about the use of concomitant medication in combination with discussions with the subject and medical record review. The site will record all concomitant medications in the appropriate sections of the pCRF.

Subjects will not be included in the investigation if they have previously been implanted with a stimulator or any implantable device in the head and/or neck or a pacemaker/ defibrillator, or if they have previously undergone sinus surgery or received treatment with therapeutic x-ray intervention in the facial region.

11.3 Subjects

11.3.1 Number of subjects

Approximately 148 subjects will be enrolled in order to achieve at least 132 subjects evaluable for the primary performance endpoint. If during the conduct of the study the drop-out rate proves to be higher than expected (>10%), enrollment will continue until at least 132 subjects were assessed for the primary endpoint.

11.3.2 Inclusion criteria

1. The subject is legally competent, has been informed of the nature, the scope and the relevance of the study, voluntarily agrees to participation and the study's provisions, and has duly signed the informed consent form (ICF);
2. Male or female aged between 18 and 65 years (inclusive) at the time of providing informed consent;
3. Diagnosed as suffering from chronic migraine with or without aura (≥ 15 headache days per month for more than 3 months before screening including at least 8 migraine days) according to the IHS classification (International Classification of Headache Disorders [ICHD]-III beta);
4. Migraine onset before the age of 60 years;
5. Reported history of migraine for at least 1 year before screening;
6. Reported stable prophylactic migraine medication regimen, if any, during the 3 months prior to screening;
7. Able and willing to maintain current prophylactic migraine medication regimen (no change in type, frequency or dose) from screening to end of follow-up;
8. Women of childbearing potential must be willing to use highly effective contraceptive methods (failure rate <1% per year when used consistently and correctly) during the study.

11.3.3 Exclusion criteria

To enter the trial, to receive treatment and continue in the clinical investigation subjects must not meet any of the exclusion criteria as indicated below.

1. Unable to distinguish between migraine headaches and other headache types;
2. Treatment with Botox in the head/neck area within 4 months of the screening visit, or planned Botox treatment during the study;
3. Previous or ongoing treatment with an implanted stimulator or other implanted device in the head and/or neck;

4. Known pronounced anterior septal deviation, or other known relevant abnormality in the nasal cavity, including bacterial infection and wounds;
5. History of relevant sinus surgery, transsphenoidal surgery for pituitary or other lesions or cerebrospinal fluid (CSF) rhinorrhea;
6. Fitted with a pacemaker/defibrillator;
7. Previously treated with therapeutic x-ray intervention in the facial region (that could have influenced the nasal mucosa);
8. Ongoing upper respiratory infection or malignancy in the nasal cavity;
9. History of regular nose bleeding (epistaxis), or concomitant condition or medication that could cause excessive bleeding including treatment with an anticoagulant;
10. Head injury or open wound that contraindicates use of the Chordate Headband;
11. Known allergy to polyvinylchloride, a material used in the Chordate Catheter, or medicinal liquid paraffin;
12. Concurrent condition or risk of non-compliance that, in the investigator's opinion, may affect the interpretation of performance or safety data or which otherwise contraindicates participation in a clinical investigation;
13. Pregnant and lactating women;
14. Participation in a clinical investigation within 3 months of enrolment or planned participation at any time during this clinical investigation;
15. Previous participation in this study;
16. Employees of the study site or the sponsor directly involved with the conduct of the study, or immediate family members of any such individuals.

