4. Known pronounced anterior septal deviation, or other known relevant abnormality in the nasal cavity, including bacterial infection and wounds;
5. History of relevant sinus surgery, transsphenoidal surgery for pituitary or other lesions or cerebrospinal fluid rhinorrhea;
6. Fitted with a pacemaker/defibrillator;
7. Previously treated with therapeutic x-ray intervention in the facial region (that could have influenced the nasal mucosa);
8. Ongoing upper respiratory infection or malignancy in the nasal cavity;

9. History of regular nose bleeding (epistaxis), or concomitant condition or medication that could cause excessive bleeding including treatment with an anticoagulant;
10. Head injury or open wound that contraindicates use of the Chordate Headband;
11. Known allergy to polyvinylchloride, a material used in the Chordate Catheter, or medicinal liquid paraffin;
12. Concurrent condition or risk of non-compliance that, in the investigator's opinion, may affect the interpretation of performance or safety data or which otherwise contraindicates participation in a clinical investigation;
13. Pregnant and lactating women;
14. Participation in a clinical investigation within 3 months of enrolment or planned participation at any time during this clinical investigation;
15. Previous participation in this study;
16. Employees of the study site or the sponsor directly involved with the conduct of the study, or immediate family members of any such individuals;

Previous and concomitant treatments

Subjects using a stable regimen of prophylactic migraine medication will be required to maintain this regimen from screening to end of follow-up and no new prophylactic treatment may be initiated during that time. Subjects on unstable dose(s) of prophylactic migraine medication(s) 3 months prior to screening will not be enrolled.

Subjects can use their regular acute (abortive) migraine medication, when necessary, during the course of the clinical investigation. However, all such use must be documented in the study specific diary.

Criteria for evaluation

Performance endpoints

Primary performance endpoint:

- Mean change from Baseline (4-week screening period) in monthly headache days with moderate to severe intensity in 4-week performance assessment period (V3 to V7).

Secondary performance endpoints:

- Mean change from Baseline in monthly headache days with moderate to severe intensity in follow-up period;
- Mean change from Baseline in monthly migraine days;

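### Exclusion criterion 5 bars only undefined 'relevant' sinus surgery, while protocol 11.2.5 and the 8.1 mitigation bar any previous sinus surgery

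*Protocol*

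**What the plan says.** Sinus surgery appears as an eligibility matter in four places in the protocol.

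- **Section 11.3.3, criterion 5:** "History of relevant sinus surgery, transsphenoidal surgery for pituitary or other lesions or cerebrospinal fluid (CSF) rhinorrhea".
- **Section 3, synopsis, criterion 5:** "History of relevant sinus surgery, transsphenoidal surgery for pituitary or other lesions or cerebrospinal fluid rhinorrhea".
- **Section 11.2.5:** a single sentence that begins "Subjects will not be included in the investigation if they have previously been implanted with a stimulator" and goes on, after other implants and pacemakers, "if they have previously undergone sinus surgery or received treatment with therapeutic x-ray intervention in the facial region".
- **Section 8.1, risk table:** the risk is introduced with "Subjects who have received radiation to the face or previous sinus surgery may have scarring and more fragile tissues", with bleeding and tissue damage during treatment as the consequence. The mitigation is "Subjects with radiation to the face or who have undergone previous sinus surgery will be excluded".

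Section 8.1 also says of this study that "eligibility criteria have been incorporated to avoid identified potential safety issues". Section 11.3.3 opens by making its list the condition for entering the trial, being treated and continuing: "subjects must not meet any of the exclusion criteria as indicated below". At Visit 1 (11.5.2), randomization is open to subjects who still satisfy the inclusion criteria and meet no exclusion criterion.

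**The concern.** The protocol gives two different rules for one safety exclusion. The narrower one, with the undefined qualifier, stands in the list that sites use to decide entry.

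What is at stake is who receives an intranasal balloon treatment. Section 8.1 ties previous sinus surgery as such to scarring and fragile tissue, and offers exclusion of those subjects as the protection. If sites apply criterion 5 as written, the protection is smaller than 8.1 tells ethics committees, authorities and investigators. Up to 11 centers (5 in Germany and at most 6 in Finland, Section 9) would also each have to decide what the qualifier means.

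**Working it through.** No figure in the plan depends on this point, so the check is a comparison of texts.

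**1. The four wordings.**

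| Place | Sinus surgery barred | Qualifier |
|---|---|---|
| Synopsis, criterion 5 | only if *relevant* | yes |
| 11.3.3, criterion 5 | only if *relevant* | yes |
| 11.2.5 | any previous | no |
| 8.1, mitigation | any previous | no |

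Two are qualified and two are not. All four are current text. The mismatch concerns 1 of the 16 exclusion criteria and 1 of the 8 rows of the 8.1 table.

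**2. Is the qualifier defined?** No section says what makes sinus surgery relevant (type, date, extent, residual scarring) or who decides.

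**3. Which text controls entry?** Section 11.3.3 refers to its own list. The screening visit (11.5.1) checks the inclusion and exclusion criteria, and Visit 1 randomizes on them. Neither step points to 11.2.5.

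**4. A test case.** Take a subject with past sinus surgery that the site considers not relevant.
- Under criterion 5 the subject is not excluded.
- Under 11.2.5 the subject may not be included.
- Under 8.1 the subject is said to be excluded.

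Both rules can be obeyed at once, and doing so gives the stricter one. The failure arises when a site uses the criteria list alone, as the visit procedures direct. Randomizing this subject would then be a deviation as Section 16.2 defines it, although every box on the list had been answered correctly.

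**5. Is the unqualified wording mere shorthand?**
- For 8.1 the evidence is mixed. The table presents itself as a summary. It keeps the qualifier for septal deviation (*pronounced*) but drops *regular* for nose bleeds, where criterion 9 has it.
- Section 11.2.5 is not a risk summary. It is phrased as a rule on inclusion. The same sentence carries over the substance of criteria 3 and 6 (implants, pacemaker or defibrillator), yet leaves out the qualifier on sinus surgery.

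**6. Exposure.** Each subject has 6 weekly treatments (11.1.1) with the balloon placed in each nostril in turn (11.2.1): 6 × 2 = 12 applications. Placebo differs only in having no oscillations (11.2.3), so insertion applies to both arms.

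**7. Statistical reach.** The sample size (13.5) rests on a difference of 3 days, SD 6, two-sided alpha 0.05 and 80% power. None of these involves the criterion. The FAS (13.1) requires treatment plus baseline and post-baseline data, not eligibility. Only the PP set could be touched, because 13.1 and SAP 3.3 give an eligibility violation as an example of a major violation. The blind data review would then have two rules to choose from for such a subject.

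**The case against.** The strongest reply is that the protocol does not actually admit these subjects. Section 11.2.5 is binding text, and a site that reads the whole protocol must apply the stricter rule. That is correct. A reader might infer that the protocol permits randomizing a subject with non-relevant sinus surgery, and the documents do not support this: it would breach 11.2.5. What stands is the practical risk, since the visit procedures direct sites to the list and the list is looser.

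Second, 8.1 is a summary and is loose elsewhere, so it is weak evidence alone. This is fair, and the textual case rests mainly on 11.2.5.

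Third, there are safeguards:
- criterion 4 (known relevant nasal abnormality);
- criterion 9 (conditions or medication that could cause excessive bleeding);
- criterion 12 (investigator's judgement);
- the ear, nose and throat examination at screening (11.4.4);
- the 8.1 rule to halt treatment on a nose bleed.

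These reduce the risk materially. They do not say which sinus-surgery rule applies. The Investigator's Brochure and the Instructions for Use might, but they are not among the documents reviewed.

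Fourth, both formal lists carry the qualifier, so clinical discretion may be intended. That is possible, and it is why the sponsor should be free to choose either rule. It does not justify leaving both in place.

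Finally, SAP 4.6 shows that the interim analysis is done, so an amendment protects only subjects not yet treated.

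**Conclusion.** The inconsistency is real and plain on the text. It is minor: a safety-eligibility mismatch in one criterion, limited by other safeguards, with no effect on the primary FAS analysis, alpha, power or sample size and at most a marginal effect on PP classification. The conclusion assumes only that some sites screen from the criteria list without cross-checking 11.2.5.

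Four stronger readings are not supported.

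- **A number of subjects.** The documents give no frequency of previous sinus surgery, so none can be stated.
- **Demonstrated harm.** Nothing shows that surgery a site would call not relevant carries the risk named in 8.1. The point is that 8.1 makes no such distinction.
- **The same fault in criterion 7.** Its parenthesis about the nasal mucosa reads naturally as the reason for excluding facial x-ray treatment, so no change is asked there.
- **Untraceable cases.** Section 11.4.5 asks for relevant past history and singles out allergies and septal deviation for separate recording. However, the item covers surgical history and draws on interview and medical records, so it cannot be inferred that sinus surgery would go unrecorded.

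**What to change.** Use one rule throughout. By default, delete *relevant* before sinus surgery in criterion 5 of 11.3.3 and of the synopsis, so that both match 11.2.5 and 8.1.

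If the sponsor intends the narrower exclusion, put the same qualified wording into 11.2.5 and the 8.1 mitigation row, so that 8.1 does not overstate the protection. Then record any previous sinus surgery at screening as a separate item, as 11.4.5 already does for septal deviation.

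The cost is a written amendment, which Section 16.1 requires for a change to eligibility and which can be bundled with the next one. The default may add a few screen failures, in a number that the documents do not allow one to estimate. The alternative gives a less favorable risk statement in 8.1 and adds one item to the medical history.
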